Data Sources and Participants: Specific Aim 2 will rely on a two pronged approach. First, we will leverage a rich, existing data resource collected as part of our recently completed community trial R01 of the WitnessCARES intervention for CRC screening (See Measures Table in Human Subjects). The data available from this study includes pre-intervention measures on a variety of psychosocial determinants of screening behavior, relevant demographic characteristics, intentions to screen both before and after the intervention, and, for a subset of participants, a 6 month follow-up report of actual screening behavior. The dataset contains 516 individuals who were: over age 50, self-identified as Black/African American, and either never screened or currently screening noncompliant. In addition to this secondary data analysis, we will collect and analyze new measures as a part of the methods described in Aim 1.

Proposed Secondary Data Analysis (Milestone 2a). The dataset from the WitnessCARES intervention study will provide us the ability to develop an initial iteration of a predictive tool to effectively identify two types of potential clients: a) individuals who, if they receive the intervention, are most likely to change from not intending to screen for CRC to intending to screen for CRC; b) individuals who intend to screen following the intervention but do not successfully convert that intention to actual engagement in screening behavior. To do so, we will use the individual items in the psychosocial and demographic measures collected pre-intervention to identify a subset of items that can successfully distinguish the types of potential clients described above. The analysis will proceed in 3 phases: variable reduction, screening intent model, and screening engagement model. *Variable Reduction:* Standard variable reduction techniques (such as principle components, missing values ratios, low variance filter, etc.) will be used to combine or exclude individual items (or sub-scales) for the candidate list of variables for model development. *Screening Intent Model:* Model development will proceed in two steps and will be based on available subjects. First, using a multivariable logistic regression model, main effects will be selected using a bootstrap backwards selection method (BBSM; alpha exit = 0.01). Second, potential two-way interactions between the selected main effects will

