be identified using the BBSM (alpha exit = 0.001). The final model estimates for predicting screening engagement will be obtained using standard bootstrap methods. *Screening Engagement Model*: The model development will proceed as described for the screening intent model, except only subjects intending to be screened will be utilized. *Model Performance*: The screening intent and engagement models will produce predicted probabilities of intent and engagement based on subject characteristics. These probabilities are relatively subjective, so the Youden's index criterion will be used to identify a cut-off for both models that identifies which clients should be identified as "intending to screen" and "screening engaged". Model performance will be summarized using the receiver operating characteristic (ROC) curve and corresponding area under the ROC curve (AUC), and the sensitivity and specificity corresponding to the Youden's index cut-offs. *Alternative Approaches*: Classification and Regression Tree (CART) or other machine learning methods may be employed for the development of a classification model. In the presence of multiple models, models will be ranked by the specified performance measures.

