Expected outcomes of Aim 1 will prove whether or not *WC Services* can achieve $\geq 65\%$ CRC screening of clients reached. **Milestone 1a:** Achieve colonoscopy by a minimum of 60 out of 200 ($\geq 30\%$) patients contacted. **Milestone 1b:** Achieve CRC stool screening for 70 of the 140 colonoscopy non-adherent clients (50% of clients refusing/ineligible for colonoscopy). Beyond these milestones, additional **feasibility benchmarks** include: a) Acceptance/satisfaction by clients per client satisfaction phone surveys; b) Acceptance/satisfaction by YourCare and MCCC per self-report and any screening metrics improvement; c) Navigation services, number of screening tests per week/month, hours spent for cost analysis; d) Acceptance/satisfaction by GI physicians and facilities per self-report, number and quality of bowel preps and no-shows; e) Process evaluation of all. **Milestone 1c:** *WC Services* will be revised based on outcomes and benchmark measures from Aim 1, to produce a new prototype to test in a larger randomized study in Phase II.

AIM 2: Proposed Data Analysis (Milestone 2b). Update the Screening Engagement Model: Utilizing standard Bayesian methods, the data collected in Aim 1 from the (expected) $n=160$ intent-to-screen clients will be used to: A) update the coefficients of the Screening Engagement Model; and B) determine whether PAM, POC and NSAP measures should be incorporated. The performance of the updated model will be assessed using the AUC, sensitivity, and specificity (with 95% confidence intervals as appropriate). If the AUC of the resulting model is 0.8 (or 0.9), indicating reasonable performance, then the corresponding 95% confidence interval width would be 0.14 (or 0.10). *FIT versus COL:* Within the sub-set of subjects that were screened, measures will be compared between those who chose FIT versus COL using the Mann-Whitney U test. In Aim 1 we expect 60 COL and 70 FIT subjects, which provides 80% power (at $\alpha=0.05$) to detect a 0.5 standard deviation difference. Additionally, a multi-variable logistic regression model may be considered to identify potential independent factors associated with screening choice.

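### The prediction models' AUC, sensitivity and specificity carry no validation or optimism correction, so as written they come from the data that built or updated the models

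*Combined protocol and SAP*

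**What the plan says.** Section 5, Milestone 2a, builds a screening intent model and a screening engagement model on the R01 data set of 516 people. The engagement model uses only those who intended to screen, and actual screening was followed up in a subset whose size is not given. After variable reduction, "main effects will be selected using a bootstrap backwards selection method", with exit level 0.01, and interactions are selected at 0.001. The bootstrap is named once more, for the final model estimates. A Youden cut-off is then chosen for each model, and "Model performance will be summarized using the receiver operating characteristic (ROC) curve and corresponding area under the ROC curve (AUC", with sensitivity and specificity at those cut-offs. Tree or other machine-learning models are optional. The ranking rule is: "In the presence of multiple models, models will be ranked by the specified performance measures".

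Section 8, AIM 2 (Milestone 2b), uses the expected 160 clients to "update the coefficients of the Screening Engagement Model" by Bayesian methods and to "determine whether PAM, POC and NSAP measures should be incorporated". Then "The performance of the updated model will be assessed using the AUC, sensitivity, and specificity", with 95% confidence intervals. On precision it takes two possible results, "If the AUC of the resulting model is 0.8 (or 0.9), indicating reasonable performance", and gives one interval width for each: "then the corresponding 95% confidence interval width would be 0.14 (or 0.10".

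Neither section names a test sample, cross-validation, a bootstrap correction of performance, or an external check.

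**The concern.** A model scored on the data that chose its predictors, coefficients and cut-off looks better than it will in new people. Aim 2 is meant to yield a tool for new clients, so new-client performance is the quantity of interest. Sensitivity and specificity suffer more than AUC, because a Youden cut-off is the point at which their sum is largest in that sample.

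Two uses of the figures are at stake. Section 8 reads an AUC of 0.8 as acceptable, and the Phase I report will carry these figures. And, if tree or machine-learning models are added, the ranking rule would pick the model carried into Phase II on a measure that rewards flexibility as well as true discrimination.

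**Working it through.** **1. The plan's own figure.** The Hanley-McNeil variance of an AUC A with n1 screened and n2 unscreened clients is

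SE² = [A(1−A) + (n1−1)(q1−A²) + (n2−1)(q2−A²)] / (n1·n2), with q1 = A/(2−A) and q2 = 2A²/(1+A).

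The outcome split is not stated; take 80 and 80.

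- A = 0.8: q1 = 0.6667, q2 = 0.7111; SE² = (0.16 + 79×0.0267 + 79×0.0711)/6400 = 0.00123; SE = 0.0351; width = 2×1.96×0.0351 = 0.138.
- A = 0.9: the same steps give SE = 0.0253 and width 0.099.

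These round to the stated 0.14 and 0.10. A 104:56 split gives 0.134 and 0.093. A half-sample hold-out of 40:40 would give 0.195 and 0.141. So the stated widths fit all 160 clients scoring a model fixed in advance, with no allowance for updating on the same clients. They argue against a large hold-out but do not exclude resampling, so they are supporting evidence only.

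**2. Size of the overstatement.** The documents do not give the signal strength, the number of candidates left after reduction, or the size of the R01 follow-up subset. The simulations therefore assume four true predictors with log odds ratio 0.4, 0.7 or 1.1 per SD (reported AUC roughly 0.65–0.75, 0.8 and 0.9), independent normal candidates, 65% screened unless stated, backward elimination at 0.01 and no interactions. Overstatement is the reported value minus the value in new clients. Youden index = sensitivity + specificity − 1.

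| Setting | Measure | 0.4 | 0.7 | 1.1 |
|---|---|---|---|---|
| 2b Bayesian update on 160 | AUC | 0.015–0.058 | 0.011–0.037 | 0.004–0.024 |
| | Youden, cut-off re-chosen | 0.097–0.178 | 0.077–0.142 | 0.062–0.117 |
| | Coverage of nominal 95% CI | 73–91% | 74–89% | 77–91% |
| 2a, n = 516 | AUC | 0.016–0.024 | 0.004–0.012 | 0.004–0.008 |
| | Youden | 0.06–0.07 | 0.04–0.05 | 0.04 |
| R01 engagement subset, assumed n = 200 | AUC | 0.05–0.07 | 0.025–0.036 | 0.01–0.02 |
| | Youden | 0.13–0.17 | 0.10–0.11 | 0.07–0.09 |

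The update rows span 36 scenarios: R01 model from 200 or 516 people, 25 candidates, 65% or 80% screened, three new measures with no effect or (at 65% screened) log odds ratio 0.4, and all of them kept or kept only if significant. The other rows span 10, 25 and 40 candidates. For example, with 25 candidates at log odds ratio 0.7, n = 516 gives 0.805 − 0.797 = 0.008 and n = 200 gives 0.805 − 0.776 = 0.029.

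Section 5 also says a similar strategy will be applied to the new data. If that meant a fresh build on 160, AUC would be overstated by 0.05–0.08, 0.035–0.06 and 0.016–0.026 at the three strengths.

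**3. Does the planned bootstrap deal with it?** Bootstrap backward selection (30 resamples, a variable kept if chosen in at least half, 25 candidates, 30–45 runs) left AUC overstated by 0.015 and 0.008 at n = 516, and 0.052 and 0.029 at n = 200 (log odds ratio 0.4 and 0.7). Bootstrapping the selection does not correct the performance figures.

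**4. Ranking.** A classification tree was compared with the logistic model when the truth is linear (n = 516 and 200, log odds ratio 0.7 and 0.4). The tree came first on same-data AUC in 0–66% of runs at depth 2, 10–98% at depth 3, 54–78% when pruned by cross-validation, and 100% at depth 5. It was truly better in 0–14%.

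**The case against.** - **The plan is silent rather than wrong.** It never says that performance is computed on the fitting data. That is so, but no other data and no correction are named, and an analyst following the text would score the models on those data.
- **The AUC error is small at the plan's target.** An excess of 0.01–0.04 compares with a confidence half-width of 0.14/2 = 0.07. True, but the error is one-sided, and interval coverage falls to 74–89%.
- **The Youden figures assume a cut-off re-chosen on the 160, which Section 8 does not state.** This stands. With the R01 cut-off carried forward the excess is about half: 0.048–0.049 against 0.104–0.110 at log odds ratio 0.7, and 0.046–0.063 against 0.129–0.142 at 0.4. The average excess for sensitivity or specificity alone is half the Youden figure.
- **The ranking result depends on tree depth, and trees are optional.** This also stands. With a threshold or interaction truth at n = 516, same-data ranking chose correctly in 96–100% of runs, against 78–100% for cross-validation.
- **Cross-validation has its own bias.** At n = 200 and log odds ratio 0.7, five-fold cross-validation read 0.751 against a true 0.775 (−0.024), close in size to the uncorrected +0.029. This bears on which correction to use, not on whether to correct.
- **Stakes are low.** No milestone has an AUC threshold, and the prototype goes on to a Phase II test. That limits the harm, but later testing does not correct the Phase I report.

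**Conclusion.** The concern holds. As written, the plan's AUC, sensitivity and specificity are same-data figures and will be optimistic. For the 2b update near AUC 0.8 the likely picture is a reported 0.79–0.83 against 0.77–0.81 in new clients. The Youden index is overstated by 0.08–0.14 with a re-chosen cut-off and by about 0.05 with a carried-forward one. For models built on all 516 people the AUC error is minor; it grows if the engagement subset is small or the signal weak. All sizes rest on the assumed signal, independent candidates and no interactions, and are illustrative. The omission itself rests on the text alone. It should be fixed before analysis, though the feasibility results of Aim 1 do not depend on it.

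**What to change.** 1. Report AUC, sensitivity and specificity corrected by resampling. Each resample should repeat variable reduction, selection or updating (including the decision on the new measures, with the R01 prior held fixed), any tuning and any choice of cut-off. For the updated model, bootstrap optimism correction brought mean AUC within 0.013 of the new-client value in all 36 scenarios, though it left 0.00–0.05 of Youden excess.
2. State whether the Youden cut-off is re-chosen on the 160 or carried over from R01.
3. Rank competing models only on cross-validated measures. Under the linear truth, repeated five-fold cross-validation picked the better model in 98–100% of runs in three of the four settings and in 68–78% in the hardest (n = 200, log odds ratio 0.4), where same-data ranking managed 12–46%.
4. Base the confidence interval on the resampling. Shifting the nominal interval by the estimated optimism raised coverage to 81–95%, which is better but not always nominal.
5. Optionally, before updating, report the AUC of the unchanged R01 engagement model in the 160 clients. In simulation its mean was within 0.01 of its new-client value.

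The cost is two or three sentences and computing time, with no change to data collection. Reported performance will be lower, cross-validation will read somewhat low in small samples, and it may less often pick a tree that really is better.

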6 TARGET ACCRUAL AND STUDY DURATION

From a list of approximately 2000 unscreened individuals from insurer and primary care patient lists (acquired through a Business Association Agreement), we will contact and enroll a maximum of 200 participants. Accrual is expected to take up to 2 years.

7 SUBJECT SELECTION

Recruitment and Informed Consent. Witness CARES, LLC staff members will work with our customer clients (YourCare and MCCC) to obtain Business Association Agreements in order to call, recruit and consent clients from their "gaps in care" lists. Information sheets and oral consent over the phone will be used in order to conduct the telephone survey that collects information to contribute to the outcomes and predictor tool development. The Business Agreements will provide coverage for offering the navigational services.

The key elements of the informed consent procedure which will be explained to the participants are: 1) the research status of the study- particularly the survey; 2) the prospect of psychological risk and the provisions for it; 3) the lack of guarantee of benefit from participation in the survey, 4) the confidentiality of subjects responses to all study measures; 5) the voluntary nature of the study; 6) the lack of consequences to medical care of the decision to consent or to refuse to participate in the survey (all participants will be offered CRC screening regardless of the

decision to complete the telephone survey); 7) the receipt of the gift card for participating in the survey interview, and 8) the freedom to withdraw from the study or to refuse to answer specific questions at any time.

Before the survey is conducted, staff members will explain: 1) the nature and purpose of the research endeavor, 2) that participation in the research component is completely voluntary, and 3) that data collected from participants will be confidential and assessed, evaluated and reported as aggregate data, as well as precautions taken in the storage of the data. The study staff member will verify that the women and men who wish to participate meet the study's eligibility criteria as described below. The staff member will solicit and respond to any and all inquiries.

For the colonoscopy procedures, individual, hospital/facility/physician specific consents will be signed and this is beyond the scope or responsibility of Witness CARES, LLC or the study staff.

7.1 Inclusion Criteria

Witness CARES, LLC will develop and obtain business agreements with YourCare and Mercy Comprehensive Care Center (MCCC) as required by these businesses to allow them to provide lists of their clients who are ages 50 and over and are non-adherent to CRC screening over the past year (i.e., no stool testing in past 11 months or colonoscopy for over 9 years). The clients will be Medicaid or Medicaid/Medicare subscribers. Uninsured patients may be included from MCCC, but will only be eligible for services to obtain FIT tests through the NYS Cancer Services Program.

7.2 Exclusion Criteria

Any participants from the lists of gaps in care clients from insurance or primary care practices who report having had a colonoscopy in the past 9 years (or having positive findings such as polyps, 5 years) or having completed some type of fecal test for CRC will be excluded. Participants under 50 will be excluded unless they have been deemed high risk by their physician, and have a prescription for CRC screening. Participants symptomatic for CRC will be excluded from the study, but will be referred for follow-up and colonoscopy.

7.3 Inclusion of Women and Minorities

The research outlined in this proposal will involve lower socioeconomic and African American clients as CRC screening is lowest in these groups. We will enroll up to 200 men and women in this study (including any race/ethnicity). We hope to enroll equal numbers of men and women.

8 STATISTICAL ANALYSIS METHODOLOGY

AIM 1: Assessment and Evaluation. After Navigators have contacted and assessed client CRC screening needs by phone for providing WC Services, they will invite and consent clients to complete the study survey to collect prospective predictor assessment measures for which participants will be incentivized with a \$20 retail gift card, a method we have found successful in previous studies. A process and system for contacting, monitoring and then assessing satisfaction of clients with services will be conducted based on current mammography services. Witness CARES, LLC will be establishing a new and more comprehensive appointment scheduling monitoring system for this feasibility study to enhance measures currently used by NWP in order to improve the ability to track and document all CRC screening services and outcomes for future development. We currently have metrics for navigation and screening that will be revised for colonoscopy and stool test navigation and colonoscopy appointment

scheduling. We will use current tracking measures for accruals and outcomes and assess these weekly and monthly. We will closely monitor number of client contacts and time requirements to determine potential cost effectiveness and feasibility measures. Colonoscopy and FIT completion will be monitored and then validated by YourCare and MCCC. Basic frequencies and descriptive statistics will be used for this analysis. We will compare outcomes from YourCare and MCCC clients. Upon completion of CRC screening, satisfaction surveys will be conducted by Call Center staff for at least 60% of clients in order to assess *WC Services* acceptability, merit and suggestions for revisions. If clients prefer, these satisfaction surveys can be sent via Survey Monkey and completed on Smartphones. The Call Center will also obtain brief satisfaction and assessment surveys from GI practices and Primary Care Physicians treating Medicaid clients referred through *WC Services*.

Expected outcomes of Aim 1 will prove whether or not *WC Services* can achieve $\geq 65\%$ CRC screening of clients reached. **Milestone 1a:** Achieve colonoscopy by a minimum of 60 out of 200 ($\geq 30\%$) patients contacted. **Milestone 1b:** Achieve CRC stool screening for 70 of the 140 colonoscopy non-adherent clients (50% of clients refusing/ineligible for colonoscopy). Beyond these milestones, additional **feasibility benchmarks** include: a) Acceptance/satisfaction by clients per client satisfaction phone surveys; b) Acceptance/satisfaction by YourCare and MCCC per self-report and any screening metrics improvement; c) Navigation services, number of screening tests per week/month, hours spent for cost analysis; d) Acceptance/satisfaction by GI physicians and facilities per self-report, number and quality of bowel preps and no-shows; e) Process evaluation of all. **Milestone 1c:** *WC Services* will be revised based on outcomes and benchmark measures from Aim 1, to produce a new prototype to test in a larger randomized study in Phase II.

AIM 2: Proposed Data Analysis (Milestone 2b). Update the Screening Engagement Model: Utilizing standard Bayesian methods, the data collected in Aim 1 from the (expected) $n=160$ intent-to-screen clients will be used to: A) update the coefficients of the Screening Engagement Model; and B) determine whether PAM, POC and NSAP measures should be incorporated. The performance of the updated model will be assessed using the AUC, sensitivity, and specificity (with 95% confidence intervals as appropriate). If the AUC of the resulting model is 0.8 (or 0.9), indicating reasonable performance, then the corresponding 95% confidence interval width would be 0.14 (or 0.10). *FIT versus COL:* Within the sub-set of subjects that were screened, measures will be compared between those who chose FIT versus COL using the Mann-Whitney U test. In Aim 1 we expect 60 COL and 70 FIT subjects, which provides 80% power (at $\alpha=0.05$) to detect a 0.5 standard deviation difference. Additionally, a multi-variable logistic regression model may be considered to identify potential independent factors associated with screening choice.

Expected Outcomes. **Milestone 2a:** Develop models based on R01 data to predict intent and CRC screening behaviors. **Milestone 2b:** Revise this R01 model incorporating new measures collected prospectively with 80% of clients contacted ($n=160$) to identify variations for likelihood of FIT v. COL completion. From these analyses we will produce a new prototype of a Screening Engagement Model to test in a larger trial for a Phase II study. **Milestone 3:** Phase I Report will be prepared to include all Milestones and feasibility benchmarks.

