5 METHODOLOGY

[figure not shown]
Overview. This Phase I small pilot efficacy and feasibility application is built upon the combined passion, persistence, science, expertise and experience from the following: a) Research on navigation for CRC screening (R01 CA 120658, [name], see Bio);²⁵ b) Years of community-based studies ([name], [name], [name], see Bios)^{10,16,26} resulting in the National Witness Project® (NWP) not-for-profit; c) Ability of the NWP to garner contracts for services from health insurance companies and health care providers (see Facilities and Resources); d) Results from our R01 (CA171935, MPIs: [name], [name], [name], see Bios);^{19,20,23} and e) Training through the NCI SPRINT Supplement ([name], [name], see Bios).²⁷ Based on this foundation, we now

are in a position to determine if we can combine this experience, data and expertise into a deliverable product (*WC Services*) that provides acceptable and appropriate services to non-adherent Medicaid clients resulting in effective CRC screening rates to meet the various requirements of health insurers (i.e., YourCare), primary care practices (Mercy Comprehensive Care Center- MCCC) and gastrointestinal endoscopy providers.

Product Concept. The proposed framework for services based on previous research^{19,28} is displayed in Figure 1. Encrypted lists of eligible clientele will be given to racially-concordant, call-center staff, including experienced navigators, according to established procedures by NWP. Scripts, based on [name]'s CRC screening protocol, will be used by navigators and call-center staff, including messaging and information that promotes positive affective associations with colonoscopy. From initial assessments and client responses, navigators will determine next steps following cues and flow chart experience (see Figure 1).

Based on assessments in real time, navigators will offer to send appropriate materials, messages and videos to clientele electronically and or by mail as requested to assist with clients' decision-making if they are not prepared for either colonoscopy or stool tests, and will be followed up by phone within two weeks. For clients

Figure 1. Framework for WC Services

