- 3) For clients planning to be screened, the navigators will begin the process of working through the services needed by the client (for either completion of the stool test) or the colonoscopy to include some or all of the following: a) delivery of a FIT or Cologuard test (dependent on Medicare coverage); b) telephone followup and assurances that stool test is completed, mailed and results are received; c) assistance to obtain the Rx for colonoscopy; d) determination of acceptable GI physician and screening location for colonoscopy; e) appointment for colonoscopy is made; f) education for and assistance with the prep materials and telephone followup for assurance that the materials are purchased (or we deliver them), the client understands the procedure; questions are answered; g) transportation plans are secured if needed, including escort or family member to accompany client; h) telephone followup the day before scheduled colonoscopy to assure prep is/will be completed; i) assistance as needed to transport the client for the colonoscopy appointment; j) telephone followup to assess client satisfaction with the procedure and understanding of results.
- 4) For clients reluctant to be screened, or who do not complete stool tests or colonoscopy appointments, navigators will conduct additional follow-up and motivational interviewing to encourage completion. After 3 attempts, the navigator will obtain permission from the client to mail them additional information and how to contact the navigator for future assistance, and then the client will be removed from the active list for navigation.
- 5) All clients reached will be invited to complete a ~130-item survey (based on measures from our R01 CRC study plus two new measures – see Table 1) to obtain answers to questions that will be analyzed to study how to more accurately predict CRC screening compliance. Clients will be offered a \$20 gift card as an incentive for completing this survey by the navigator over the phone.
- 6) Following successful CRC screening (fecal test or colonoscopy), clients will be contacted by telephone to assess qualitative measures of satisfaction with the navigational services as well as the screening services received. These findings will be used to refine and revise the WC Services.

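### Client satisfaction (feasibility benchmark a) is exposed to courtesy bias, because nothing stops the navigator who served a client from conducting that client's satisfaction interview

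*Combined protocol and SAP*

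**What the plan says.** **Who delivers the service.** Section 5, Product Concept, says that "Encrypted lists of eligible clientele will be given to racially-concordant, call-center staff, including experienced navigators". The service scripts "will be used by navigators and call-center staff".

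**Who measures client satisfaction.** Section 8, Aim 1, says that "satisfaction surveys will be conducted by Call Center staff for at least 60% of clients", after screening is complete. The purpose is to judge how acceptable the service is and to gather ideas for changing it. The alternative is optional: "If clients prefer, these satisfaction surveys can be sent via Survey Monkey and completed on Smartphones". Benchmark (a) in the same section is nevertheless defined by telephone surveys.

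**The navigation steps.** In section 9, the navigators' own list of services ends at step 3(j) with "telephone followup to assess client satisfaction with the procedure and understanding of results". Step 6 covers satisfaction with the navigation itself, by telephone after successful screening, and does not name the caller.

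**Who surveys the practices.** Section 8 adds that "The Call Center will also obtain brief satisfaction and assessment surveys from GI practices and Primary Care Physicians". Benchmark (d) combines self-report from GI physicians and facilities with bowel-preparation and missed-appointment data.

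**Safeguards.** Section 10 keeps names out of the satisfaction data. Section 8 has the insurer and the clinic validate screening completion. Neither section describes a separate collector for satisfaction.

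**The concern.** People tend to rate a service more kindly when the person asking is the one who provided it. Here the interviewer may be the navigator who arranged the client's appointment, preparation or transport. Leaving names out of the data file does not help, because the interviewer still hears the answer. The online form would help, but a client gets it only on stating a preference, so its users select themselves.

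At stake is research question (a) in section 4, whether those using the services find them usable and valuable, and the revision of the service under Milestone 1c. The survey is meant to bring out what should change, and criticism is what a client is least likely to voice to the person who helped. That holds whether satisfaction is scored as a percentage or recorded in words.

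**Working it through.** **Inputs from the documents**

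- Expected screened clients (section 8): 60 by colonoscopy and 70 by stool test, out of 200 contacted.
- Survey coverage (section 8): at least 60%.
- Analysis (section 8): descriptive only. No scale, threshold or precision is given for satisfaction.

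**Assumptions, not in the documents**

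- Satisfaction is summarised as a proportion, between 70% and 95%. Section 9 calls the measures qualitative, so this is a choice made for the check.
- Upward bias is 2, 5 or 10 points.

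**Step 1: the plan's own figure.** (60 + 70)/200 = 130/200 = 65%. This reproduces the section 8 target.

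**Step 2: respondents.** 0.60 × 130 = 78. If all 200 contacted clients were the base, 0.60 × 200 = 120; but section 9, step 6, limits the survey to screened clients, so 78 is the better reading.

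**Step 3: sampling error.** The 95% half-width is 1.96 × √(p(1 − p)/n).

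| Proportion satisfied | Standard error, n = 78 | Half-width, n = 78 | Half-width, n = 120 |
|---|---|---|---|
| 70% | 5.2 points | 10.2 points | 8.2 points |
| 80% | 4.5 | 8.9 | 7.2 |
| 90% | 3.4 | 6.7 | 5.4 |
| 95% | 2.5 | 4.8 | 3.9 |

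Example: at 80%, √(0.80 × 0.20/78) = 0.0453, and 1.96 × 0.0453 = 0.089.

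**Step 4: bias against sampling error.** With n = 78, a bias equals one standard error at about 2.5 to 5 points and the full half-width at about 5 to 10 points. Suppose true satisfaction is 80% and the reported rate is 80% plus the bias. The exact binomial coverage of the Wilson 95% interval is then:

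| Bias | Coverage of the true 80% |
|---|---|
| 0 points | 95.4% |
| 2 points | 94.7% |
| 5 points | 84.5% |
| 10 points | 37.8% |

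So 2 points is negligible, 5 points is noticeable, and 10 points makes the interval misleading.

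**Step 5: benchmark (d).** The number of practices is not given. If it were 5, 10 or 20 with 80% satisfied, the Wilson half-widths would be about 29, 23 and 17 points. These counts are illustrative only. They show that the client calculation cannot be carried over to the practices.

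**The case against.** **The roles may already be separate.** Section 8 has navigators contact, assess and consent clients, and Call Center staff conduct the satisfaction surveys. Section 5 also names navigators and call-center staff side by side. On that reading the plan is close to the fix already. This stands in part: a reader might infer that navigators will routinely interview their own clients, and the documents do not say so. But section 5 also counts navigators among the call-center staff, and no sentence rules the overlap out. Step 3(j) puts a satisfaction question in the navigators' list, although about the procedure rather than the navigation.

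**The size of the bias is unknown.** A reader might infer that the benchmark does carry a bias as large as its sampling error. The documents do not support that. They give neither a bias nor a satisfaction rate, and at 85% satisfied with n = 78 the half-width is 7.9 points, so even a 5-point bias would fall short of it. Only exposure is established.

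**Benchmark (d) differs.** A reader might extend the argument to it in full. Part of (d) is bowel-preparation and missed-appointment data, which are not ratings. Practices are not the recipients of navigation, and their number is unknown. This objection stands.

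**Little hangs on the figure.** No go/no-go rule uses a satisfaction percentage. Milestone 1c draws on many other measures, and an advisory board reviews feasibility (section 5, Study Team). This limits the consequence but does not remove the exposure.

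**A larger uncertainty lies elsewhere.** Only screened clients are surveyed, and perhaps only 60% of them. If 90% of 78 are satisfied, the value for all 130 could lie between 0.90 × 78/130 = 54% and (0.90 × 78 + 52)/130 = 94%. That is true and is a separate matter; changing the caller does not address it.

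**Conclusion.** The point holds as a minor, inexpensive improvement to benchmark (a). The same call-center group may both deliver the service and ask clients to rate it, and the plan has no rule or recorded variable that would prevent or reveal an interviewer effect.

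Its size cannot be stated from the documents. If satisfaction is treated as a proportion, a bias of about 5 to 10 points would match the 95% half-width at 78 respondents, and one of about 2 points could be ignored. For benchmark (d), the conclusion is limited to its self-report component, with no claim about magnitude. Milestones 1a and 1b are unaffected, because they count completed screening, which the insurer and the clinic validate.

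**What to change.** In section 8 (Aim 1, Assessment and Evaluation), and for the satisfaction questions in section 9, steps 3(j) and 6:

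1. State that the satisfaction call is made by a call-center member who did not navigate that client.
2. Keep the Survey Monkey form as an option, but offer it to every client rather than waiting for a preference to be voiced. Making it the default is not needed: the documents give no online response rate for this population, so the effect on the 60% target cannot be judged.
3. Record the mode and an interviewer code for each survey.
4. Report satisfaction by mode descriptively, and say that mode is self-selected, so a difference between modes is not an estimate of the bias.

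The cost is a call-assignment rule, a line in the script and two data fields. Scheduling becomes slightly less flexible, and some rapport is lost when a different person calls. No added staff should be needed if there is more than one caller, as the plural wording in section 5 suggests. The staffing detail is in a budget document that is not part of this file, so that should be confirmed.
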